### Effects of Midodrine on BP, CBF and Cognitive Performance in Persons with SCI

In 2006 The VA RR&D Service renewed [name] CoE (#B4162C), and a component of the Cardiovascular Autonomic Program within the CoE was entitled "Determination of the Efficacy of an  $\alpha$ -Agonist on BP and CBF in Patients with Tetraplegia". The results of this initiative have been published in two manuscripts. We documented an increase in BP and an attenuated fall in CBF during head-up tilt in persons with SCI following midodrine 10 mg administration. In addition, a portion of [name] CDA II award (#A6161W) was determined the effect of midodrine (10 mg) on 4-hour seated BP, CBF and performance on a serial subtraction task in hypotensive individuals with SCI.

Data collection is ongoing but testing is complete in 14 individuals with lesions from C3-T4. There was a significant increase in seated BP from the baseline (BL: 90±12/58±11 mmHg) to the 4-hour post drug (midodrine) average (119±18/76±14 mmHg; p<0.0001) and a statistically significant increase in CBF (39±9 to 44±11 cm/sec, respectively; p<0.01). Further the relationship between the change in SBP and the change in MFV following administration of midodrine was statistically significant (Figure 3). To address the impact of significant increases in SBP and CBF on cognitive performance subjects performed a serial subtraction task, to assess intellectual efficiency, before and after midodrine administration. Following midodrine administration the number of attempts was increased from BL (50.7±29.6 vs. 43.2±28.2, respectively; p<0.05), and the number of correct response was also significantly increased (44.6±30 vs. 40.0±28.7, respectively; p<0.05) in subjects with SCI.

Although these data suggest that improved cognitive performance may be associated with elevation in BP and CBF following midodrine administration, this work was performed in a relatively small number of subjects, and the multiple regression model between physiological increases (i.e., change in BP and CBF) and cognitive improvements (i.e., # correct responses after drug) was not statistically significant ( $r^2=0.264$ ; p=0.19).

[figure not shown]
Figure 3  
 $r^2=0.276$ ; p<0.05

The relationship between the change in systolic BP and the change in mean flow velocity (MFV) from seated baseline to the average of the 4-hour seated observation after administration of midodrine.

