**Pre- and Post -Treatment Visits** – Within 1 week of determining the appropriate dose of midodrine for each subject, eligible participants will return to the laboratory for pre-randomization testing including: (1) laboratory BP and heart rate (HR) assessments, (2) CBF measurement at rest and during cognitive testing, (3) cognitive testing, (4) mood and QOL surveys, (5) 24-hour ambulatory BP monitoring and (6) 24-urine volume. Subjects will arrive at the laboratory between 10AM and 1PM after a 4 hour fast, and having avoided alcohol, caffeine, and nicotine for 12-hours. Subjects will remain in their wheelchair for instrumentation, which will include: 1) electrocardiogram (ECG): three surface electrodes will be applied to the chest for continuous 3-lead recording of heart rate (HR); 2) brachial BP: will be monitored using a manual sphygmomanometer and finger arteriolar beat-to-beat BP will be recorded using a photoplethysmograph placed around the middle and index fingers of the left hand; 3) CBF: will be monitored and recorded from the right and left middle cerebral artery (MCA) using transcranial Doppler ultrasound technology. Subjects will remain in the seated position for 30 minutes of baseline (BL) data collection; HR, BP, CBF will be monitored continuously for 5-minutes at 0, 10 and 20 minutes, brachial BP will be monitored and recorded at 30-second intervals during each of the 5-minute data collections periods. After the BL assessments subjects will be asked to participate in a complete neuropsychological battery (Appendix 7) which will include assessments of: pre-morbid intellectual abilities, attention & concentration, information processing, memory, and executive control. The NP battery will take

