#### **Study Objective s:**

Based on our pilot data we believe that the proportion of individuals classified as normotensive will be increased after 30-days of treatment with midodrine compared to those treated with placebo. We plan to classify individuals as normotensive if SBP is within the target range of 111-139 mmHg for  $\geq 50\%$  of the 24-hour observation (i.e., about 60 BP recordings) during the post-treatment period and the post-treatment relative risk of hypotension in the midodrine group versus placebo group will be assessed. Relative risk will be

determined by casting raw data into simple counts in a 2x2 contingency table, from which the proportion of cases that are classified as hypotensive in the midodrine group will be divided by the proportion of hypotensive cases in the placebo group. The 95% confidence interval for the relative risk value will be constructed, as described by Newcombe and Altman. In addition, clinical relevance will be quantified by calculating the number needed to treat (NNT) from the relative risk calculation as follows:  $NNT = 1 / (\text{hypotension rate in midodrine group} - \text{hypotension rate in placebo group})$ .

We hypothesize that, during a typical 24-hour day, the proportion of SBP observations within the target range of 111-139 mmHg will be increased after treatment with midodrine compared to placebo, after controlling for the baseline proportion. We anticipate that about >50% of the subjects randomized to midodrine will have normal 24-hour SBP after 30-days of treatment. In contrast we expect < 25% of individuals randomized to receive placebo to have normal 24-hour SBP after the 30-day intervention. If our postulated values are accurate, the relative risk for hypotension for the subjects on midodrine would be ~0.67, which represents about a 33% reduction in the rate of hypotension in subjects treated with midodrine compared to those randomized to placebo. The resulting NNT is ~ 4, which suggests that about 4 subjects with SCI would need to be treated with midodrine to normalize BP in one subject.

We will then determine the effect of increasing SBP to normal levels on the following outcome parameters:

Cerebral Blood Flow:

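### The only BP comparison with a named method is a twice-dichotomised 2x2 relative risk; no analysis estimates the between-arm difference in 24-hour SBP in mmHg

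*Combined protocol and SAP*

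**What the plan says.** Under Data and Statistical Analysis, Study Objectives, a subject is normotensive after treatment if SBP lies in 111-139 mmHg "for $\geq 50\%$ of the 24-hour observation (i.e., about 60 BP recordings"). The comparison of arms is then set out: "Relative risk will be" "determined by casting raw data into simple counts in a 2x2 contingency table", with a 95% confidence interval and an NNT.

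The planning values follow: "We anticipate that about >50% of the subjects randomized to midodrine will have normal 24-hour SBP after 30-days of treatment", whereas "we expect < 25% of individuals randomized to receive placebo to have normal 24-hour SBP". From these the plan concludes that "the relative risk for hypotension for the subjects on midodrine would be ~0.67" and that the NNT is about 4.

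The same section also hypothesises that the proportion of readings in the target range will be higher on midodrine than on placebo, controlling for the baseline proportion. It gives no model and no effect measure for this.

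For CBF, cognition and mood/QOL the plan names ANCOVA with the pre-randomisation value as covariate. It names none for BP. The recordings exist: the Pre- and Post-Treatment Visits include "5) 24-hour ambulatory BP monitoring". The preliminary work reported BP in mmHg, as a "significant increase in seated BP from the baseline" (SBP 90±12) to the 4-hour average after drug (119±18).

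**The concern.** SBP is continuous, and the relative risk discards information twice. A subject with 49% of readings in range counts the same as one with none. With only two categories, a subject mostly above 139 mmHg falls on the side that the plan then calls hypotensive, together with one who did not respond at all.

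The BP rise is the step on which the other hypotheses rest. The Preliminary Studies section says the data should help power a larger trial of sustained BP elevation. The analysis section says a similar proposal was not funded for lack of convincing data linking increased BP on extended midodrine to CBF and test performance. As written, the trial would report effects on CBF and cognition beside a coarse BP comparison that is likely to be inconclusive. It would give no between-arm BP difference in mmHg and no SD for planning.

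**Working it through.** **Inputs from the plan.** Normotensive 50% (midodrine) and 25% (placebo); 20 per arm with 10% attrition; about 60 readings per subject. No significance level or power target is stated for BP. I take two-sided 5%, in line with the 95% interval.

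**The plan's own figures.**
- Completers: 40 × 0.90 = 36, or 18 per arm.
- Relative risk of hypotension: (1 − 0.50)/(1 − 0.25) = 0.667.
- NNT: 1/|0.50 − 0.75| = 4. The formula as printed gives −4; the magnitude agrees.

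**Interval at exactly the planned rates.** Expected hypotensive counts are 9 of 18 and 13.5 of 18. The log-RR standard error is √(1/9 − 1/18 + 1/13.5 − 1/18) = √0.0741 = 0.272. The interval is exp(−0.405 ± 1.96 × 0.272), about 0.39 to 1.14, which includes 1.

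**Power of the 2x2, by exact enumeration at 18 per arm.** Fisher 0.24; log-RR interval excluding 1, 0.29; uncorrected chi-square 0.37.

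**The same difference on a normal scale.** Read 25% and 50% as one cut of a normal variable: d = z(0.50) − z(0.25) = 0.6745. The noncentrality is d × √(18/2) = 2.02 on 34 df, giving t-test power 0.50. For ANCOVA, d becomes d/√(1 − r²) on 33 df:

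| Pre/post correlation r (assumed) | Effect in residual SDs | Power |
|---|---|---|
| 0.3 | 0.707 | 0.54 |
| 0.5 | 0.779 | 0.62 |
| 0.7 | 0.945 | 0.79 |

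By the normal approximation, 80% power needs 58 per arm for the 2x2 and 35 per arm for the unadjusted continuous comparison.

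**Reading-level simulation.** This used 60 readings per subject, 18 subjects per arm and 1,500 runs per setting, with arm means set to give 25% and 50% normotensive. The SDs are assumptions: between-subject 8 to 18 mmHg, within-subject 10 to 15 mmHg.

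| Analysis | Between-subject SD 8-12 | SD 18 |
|---|---|---|
| 2x2, chi-square | 0.36-0.39 | 0.37 |
| Mean SBP, t-test | 0.49-0.56 | 0.77-0.78 |
| Mean SBP, ANCOVA, r = 0.5 | 0.59-0.66 | 0.87 |
| Share in range, ANCOVA, r = 0.5 | 0.53-0.55 | 0.58 |
| Mean SBP, ANCOVA, r = 0.7 | 0.78-0.80 | 0.97 |
| Share in range, ANCOVA, r = 0.7 | 0.65-0.72 | 0.61 |

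A separate set of runs gave 0.52 to 0.57 for the share in range at r = 0.5.

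The SD 18 column needs care. Reaching 50% normotensive there took arm means of 100.25 and 117.25, a gap of 17/18 = 0.94 SD. At that midodrine mean, 1 − Φ((139.5 − 117.25)/18) = 1 − Φ(1.24), or about 11% of subjects, average above the range. Part of the power is therefore overshoot.

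**Precision in mmHg.** Without baseline adjustment, the 95% half-width is 2.03 × SD × √(2/18). That is 8.1 mmHg at SD 12 and 12.2 mmHg at SD 18, taking the two pilot SDs as a range. The pilot data were seated, 4-hour and uncontrolled, so the 24-hour SD may differ.

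**The case against.** - **The relative risk is not the whole BP plan.** A reader might infer that it is the only BP comparison. The documents do not support that: the share-of-readings hypothesis is graded, baseline-adjusted and free of the 50% cut. Against an ANCOVA on that share, mean SBP gains only about 6 to 11 points at r = 0.5 for SDs of 8 to 12. This stands. What is missing is a named model and estimate, and the share still yields no mmHg effect.
- **The power loss depends on the comparator.** A reader might infer that power is roughly halved. Chi-square against an unadjusted t-test (0.37 against 0.50) loses about a quarter, and the log-RR interval (0.29 against 0.50) about two-fifths. Halving needs Fisher's test, which the plan does not name, or an ANCOVA with an assumed r, where part of the gain comes from baseline adjustment. The log-RR interval is itself my assumption about the interval method the plan cites. This also stands.
- **The aim is normalisation.** The intervention is meant to bring SBP into 111-139 mmHg, so counting overshoot as non-success is coherent, and a mean cannot show that SBP stayed in range. The Dose Determination Visit also excludes subjects with two or more consecutive readings above 135/85 mmHg, which should limit overshoot. This stands against replacing the in-range measures, not against adding a mean difference.
- **The stakes are limited.** The stated primary objective concerns effect sizes for CBF, cognition, mood and QOL. No power target is set, and a mmHg difference could be computed later from the recordings. True, but an unplanned analysis is weaker support for the next trial than a planned one.

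**Conclusion.** The point holds as an omission that is cheap to repair. The one BP comparison with a named method cuts the data twice, the graded comparison has no model, and the between-arm BP difference in mmHg is not estimated anywhere.

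At the plan's rates the 2x2 has power of about 0.24 to 0.37, against about 0.50 on an unadjusted normal scale and 0.54 to 0.79 with baseline ANCOVA. These figures rest on 18 completers per arm, a two-sided 5% level, a normal-shift reading of 25% versus 50%, and an assumed correlation of 0.3 to 0.7. ANCOVA on the share in range would recover much of the difference.

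The documents do not support a general claim of halved power or a case for dropping the in-range classification. The larger simulated gains come from a wide between-subject SD at which overshoot contributes.

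**What to change.** In the Study Objectives:

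1. Add an ANCOVA of post-treatment 24-hour mean SBP (mmHg) on arm, with pre-randomisation 24-hour mean SBP as covariate. Report the adjusted difference, its 95% confidence interval and the residual SD.
2. Name the model for the share-of-readings hypothesis: ANCOVA of the post-treatment share in range on arm and baseline share, with the adjusted difference and its interval.
3. Keep the 50% classification, relative risk and NNT as clinical-relevance summaries.
4. Report separately, by arm, the shares of readings below 111 and above 139 mmHg, so that a mean raised by overshoot is visible.

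The cost is wording, since both recordings are already planned. The one drawback is that a mean difference does not itself show that SBP stayed in range, so items 2 to 4 must stay beside item 1.

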## Research Design and Methods

We propose to determine the effects of midodrine, administered in a randomized, double blind, placebo-controlled, outpatient trial to normalize BP over a 30-day period, on CBF, cognitive function, mood and QOL. Our primary objective is to generate pilot data describing the effect size of change in CBF, cognitive test score, mood and QOL following sustained elevation in BP, to normal levels, in hypotensive individuals with SCI.

Approximately 50 subjects with SCI will be screened for study eligibility. We anticipate that approximately 40 of the subjects screened will be eligible and will undergo a 4-hour laboratory dose-effect trial. Once dose has been determined subjects will be randomized by IVAN (Interactive Touch Tone Randomization System) to receive either midodrine or placebo for the 30-day out-patient drug treatment intervention. Randomization will occur in a double-blinded manner, and individuals that use an abdominal binder regularly will be stratified equally as will those with a positive history of traumatic brain injury (TBI). Our recruitment target is 20 subjects per randomization category. We estimate approximately 10% attrition during the 30-day out-patient treatment protocol; as such, complete data will be available in ~36 subjects. Study medication and placebo will be distributed by the James J Peters VAMC Pharmacy Service. The study is proposed to be completed in two years. Total enrollment will be accomplished within 18 months of obtaining full IRB approval, which should be complete within 6 months of funding, and subject participation is estimated to last about 6-8 weeks.

**Eligibility Criteria – Inclusion Criteria:** (1) males and non pregnant females; (2) 18 – 65 years of age; (3) chronic SCI ( $\geq 1$  year post injury); (4) ability to provide informed consent; (5) laboratory or clinical evidence of hypotension (WHO criteria - SBP  $\leq 110$  mmHg in males and  $\leq 100$  mmHg in females). **Exclusion Criteria:** (1) SBP  $> 110$  mmHg for males and  $> 100$  mmHg for females (2) documented history of: (a) coronary artery disease, (b) stroke, (c) diabetes mellitus, (d) current pregnancy or lactation, (e) cardiac arrhythmias; (f) significant systemic, hepatic, cardiac or renal illness, (g) suspected malignancy, (h) neurological disease other

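### The relative risk of hypotension counts everyone outside the target range, not only those with low pressure, and the printed NNT formula gives −4 where the text says about 4

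*Combined protocol and SAP*

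**What the plan says.** All the relevant rules are in the Study Objectives section of the combined protocol and SAP.

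- **The class that is defined.** "We plan to classify individuals as normotensive if SBP is within the target range of 111-139 mmHg for" at least 50% of the 24-hour observation, which is put at about 60 readings.
- **The class that is analysed.** Raw data go into a 2x2 table, and the "proportion of cases that are classified as hypotensive in the midodrine group will be divided by the proportion of hypotensive cases" on placebo. No rule is given for calling a subject hypotensive after treatment.
- **The worked example.** The plan expects more than 50% of midodrine subjects to be normal. For placebo it says: "In contrast we expect < 25% of individuals randomized to receive placebo to have normal 24-hour SBP after the 30-day intervention". It concludes that "the relative risk for hypotension for the subjects on midodrine would be ~0.67, which represents about a 33% reduction in the rate of hypotension".
- **The NNT.** The formula is one divided by the difference "hypotension rate in midodrine group" minus the same rate on placebo. The stated result is about 4, read as "about 4 subjects with SCI would need to be treated with midodrine to normalize BP in one subject".

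The only numerical hypotension criterion the trial adopts is for entry. The Eligibility Criteria require "laboratory or clinical evidence of hypotension (WHO criteria - SBP" at or below 110 mmHg in men and 100 mmHg in women). The Screening Visit applies it to the average seated or supine reading. It differs by sex and has no 24-hour rule, and the Study Objectives do not link it to this outcome.

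**The concern.** A 2x2 table needs two classes. With only normotensive defined, the other class becomes everyone else, and the plan calls everyone else hypotensive. Three kinds of subject, in either arm, would carry that label without mostly low pressure by the trial's own criterion:

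- a subject mostly above 139 mmHg;
- a subject with mixed readings, for example 27 of 60 in range, 21 below and 12 above (an illustration, not trial data);
- a woman mostly at 101-110 mmHg, who is below the target range but above the entry cut-off for women.

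The first kind matters most. The plan foresees high readings: the Dose Determination Visit cites preliminary responses above 139 mmHg in 17% at 10 mg, and Adverse Events Reporting lists supine hypertension as expected. Overshoot could then be tallied as the condition under treatment.

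Without a stated rule, two analysts could also build different tables, one from the complement and one from the entry cut-offs. Preliminary Studies and Data and Statistical Analysis both say the results should support a larger trial, so a mislabelled reduction in hypotension could be carried into that proposal. The NNT formula is a separate fault: followed literally, it prints a benefit as a negative number.

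**Working it through.** **Inputs.** Normal rates of 0.50 (midodrine) and 0.25 (placebo), from the Study Objectives. The plan gives them as more than 50% and less than 25%, so these are boundary values. The section Research Design and Methods expects that "complete data will be available in ~36 subjects", taken here as 18 per arm.

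**Step 1: reproduce the plan's relative risk.**

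- Complement of normotensive: (1 − 0.50)/(1 − 0.25) = 0.50/0.75 = 0.667, a reduction of 33.3%. This matches the plan.
- Relative risk of being normotensive: 0.50/0.25 = 2.0. No match.
- Its inverse: 0.25/0.50 = 0.5. No match.
- Odds ratio of the complement: (0.50/0.50)/(0.75/0.25) = 0.33. No match.

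Of these readings, only hypotensive as not normotensive gives the plan's figure.

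**Step 2: the NNT.**

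- As printed: 1/(0.50 − 0.75) = −4.0.
- With the order reversed: 1/(0.75 − 0.50) = 4.0, the stated value.

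Rates inside the plan's inequalities keep the wrong sign. For example, 60% and 20% normal give a relative risk of 0.40/0.80 = 0.50 and a printed NNT of 1/(0.40 − 0.80) = −2.5.

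**Step 3: how far a low-pressure-only measure could differ.** Let *a* (midodrine) and *b* (placebo) be the shares of all subjects in the arm counted as hypotensive but not low. The documents give neither, so the values below are assumptions.

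RR = (0.50 − a)/(0.75 − b), and NNT = 1/[(0.75 − b) − (0.50 − a)].

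| a | b | RR | NNT |
|---|---|---|---|
| 0 | 0 | 0.67 | 4.0 |
| 0.05 | 0 | 0.60 | 3.3 |
| 0 | 0.05 | 0.71 | 5.0 |
| 0.05 | 0.05 | 0.64 | 4.0 |
| 0.10 | 0 | 0.53 | 2.9 |
| 0 | 0.10 | 0.77 | 6.7 |
| 0.10 | 0.10 | 0.62 | 4.0 |

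The relative risk moves down if the misclassified subjects are on midodrine and up if they are on placebo.

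**Step 4: the same in subjects.** At 18 per arm the expected numbers out of range are 18 × 0.50 = 9 and 18 × 0.75 = 13.5 (an expectation, not a possible count), and 9/13.5 = 0.67. Moving one subject gives 8/13.5 = 0.59 (midodrine), 9/12.5 = 0.72 (placebo) or 8/12.5 = 0.64 (one in each arm).

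**Step 5: sampling error for scale.** The standard error of the log relative risk is √(1/9 − 1/18 + 1/13.5 − 1/18) = 0.272. The approximate 95% interval is 0.667 × exp(±1.96 × 0.272), or 0.39 to 1.14. Every value in steps 3 and 4 lies inside it.

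**The case against.** The strongest reply is that this is a matter of wording. The 0.67 is a planning illustration, and its authors may simply have assumed that nobody in a cohort enrolled for low pressure would end mostly above range. Dose finding re-tests high responders at a lower dose and excludes subjects with two or more consecutive readings above 135/85 mmHg. High readings are also followed in the Treatment Phase and as adverse events. The Study Objectives plan a separate comparison of the proportion of readings in range, adjusted for baseline, which needs no hypotension label. The main aims concern cerebral blood flow, cognition, mood and quality of life. The NNT sign is a slip that the stated result already corrects.

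Much of this stands. The example does not prove a deliberate rule, the size and direction of any distortion are unknown, and the other analyses are unaffected. The 2x2 is also coherent for what the plan wants to learn, since it reads the NNT as the number treated to normalize pressure in one subject.

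The defect remains. One stated rule in a two-class table leaves the complement as the only class that the section itself supplies. The dose-finding exclusion rests on 4-hour visits that assess seated systolic pressure, whereas the outcome covers 24 hours, and it does nothing about mixed readings or women at 101-110 mmHg. Neither the in-range comparison nor adverse-event capture changes the name or content of the reported relative risk. The formula still contradicts its own example.

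**Conclusion.** The concern holds and should be fixed before analysis. The plan names one outcome and counts another: the 0.67 and the 33% reduction describe failure to reach the target range, not hypotension. The NNT formula has the wrong sign, with the correct magnitude at the boundary rates.

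This is an error of meaning, not a demonstrated bias. The low-pressure-only range of 0.53 to 0.77 rests on assumed shares of 5 or 10 points and on the plan's boundary rates. The actual shares cannot be found in the documents: no sex split is given, dose finding limits overshoot to an unknown degree, and mixed readings can occur in both arms because dosing is in the daytime while readings span 24 hours.

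**What to change.** **Needed.**

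1. Rename the 2x2 outcome as not in the target range, with the existing rule written out (111-139 mmHg for at least 50% of the 24-hour readings), and label its relative risk and NNT to match.
2. Write NNT = 1/(placebo rate − midodrine rate), with both rates being proportions not in the target range.

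**Useful addition.** Report counts by arm in four exclusive classes from the same readings:

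- in range, by the plan's rule;
- hypotensive, with more than 50% of readings at or below 110 mmHg in men or 100 mmHg in women;
- above range, with more than 50% of readings over 139 mmHg;
- none of these, which takes in mixed readings and women mostly at 101-110 mmHg.

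The cut-offs are the trial's own; applying them to more than half of the 24-hour readings is a new descriptive convention and should be stated as such. If a relative risk of hypotension is quoted, compute it from the hypotensive class alone and show the above-range count beside it. Otherwise a shift above 139 mmHg would look like benefit.

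**Cost.** A few sentences and one table, from 24-hour data already collected, with no new visits. With about 36 completers some cells will be sparse, so the table should stay descriptive.

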- Analysis of covariance (ANCOVA) will be used to determine the change in CBF at rest and during cognitive testing following randomization to midodrine versus placebo. Pre-randomization CBF will be used as the covariate. Our hypothesis is that there will be a significant increase in CBF, both at rest and during cognitive testing, after 30-days treatment with midodrine compared to placebo.

Memory and Attention Processing :

- ANCOVA will be used to determine the change in cognitive function from baseline to post-treatment following randomization to midodrine versus placebo, using the pre-randomization t-score as the covariate. Our hypothesis is that there will be a significant improvement in cognitive function in individuals treated with midodrine as assessed by standardized cognitive tests of memory and attention & processing speed compared to those randomized to placebo.

Depression, Anxiety and Fatigue :

- ANCOVA will be used to determine the change in mood and QOL score from baseline to post-treatment following randomization to midodrine versus placebo, using the pre-randomization QOL score as the covariate. Our hypothesis is that there will be a significant improvement in QOL in individuals treated with midodrine as assessed by the BPQOL compared to those randomized to placebo.

Adverse Events Reporting :

- To determine the differences in AEs reported at the end of 30-days treatment following randomization to midodrine versus placebo. Our hypothesis is that there will be an increase in mild and moderate drug-related AEs in individuals treated with midodrine compared to those on placebo. A few AE's may be expected to include supine hypertension (may not have been present prior to drug **administration**), **exacerbation of AD (elevated BPs recorded during known trigger's for AD, such as bowel care, bladder distension, transfers), pruritis, urinary retention and more severe or more frequent headaches.**

Secondary Analyses :

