- Our conceptual model is that prescription medication class, use of support stockings, abdominal binders and history of TBI may function as mediator variables between SCI and the dependent variables. To explore this mediation, at a first level of analysis we will examine the bivariate relationships between the mediator and dependent variables. Second, we will build hierarchical multiple regression models in which a potential mediator variable and SCI status (dummy coded) are both forced into the model. In addition, examination of the partial correlation between SCI and dependent variables (after partialing out the effect of the mediators relative to the zero order correlation will provide insight into the effect size.

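### Randomisation is stratified by abdominal-binder use and TBI history, but each ANCOVA adjusts only for baseline, so precision is lost if either factor predicts the outcome beyond baseline

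*Combined protocol and SAP*

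**What the plan says.** **Randomisation.** Under Research Design and Methods, the combined protocol and SAP states that "individuals that use an abdominal binder regularly will be stratified equally as will those with a positive history of traumatic brain injury (TBI"). The target is 20 subjects per arm. With about 10% attrition, "complete data will be available in ~36 subjects".

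**Purpose.** The same section states: "Our primary objective is to generate pilot data describing the effect size of change in CBF, cognitive test score, mood and QOL".

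**Analysis.** Under Study Objectives, three ANCOVA entries compare midodrine with placebo, and each names one covariate:

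- CBF at rest and during testing: "Pre-randomization CBF will be used as the covariate"
- Cognition: "using the pre-randomization t-score as the covariate"
- Mood and QOL: "using the pre-randomization QOL score as the covariate"

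**Other use of the factors.** They reappear only under Secondary Analyses, where "abdominal binders and history of TBI may function as mediator variables" between SCI and the dependent variables. In those regressions, "a potential mediator variable and SCI status (dummy coded) are both forced into the model". Treatment arm is not named there.

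**The concern.** Stratified allocation makes the arms more alike on the two factors. If the factors are prognostic, this reduces the true sampling variability of the treatment difference. A model that omits them cannot credit that reduction, because their contribution stays in the residual variance. The reported standard error then exceeds the true one and the test rejects too rarely.

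The Secondary Analyses do not fill the gap. They pair a potential mediator with SCI status and contain no treatment term, so they cannot adjust the midodrine-versus-placebo estimate. If SCI status means presence of SCI, it is also constant, because chronic SCI is an inclusion criterion.

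At stake is the precision of the study's main product. The stated purpose is to describe effect sizes from about 36 completers. Under Data and Statistical Analysis, the sponsor says that an earlier proposal was not funded for want of convincing preliminary data and that this study is meant to support a large trial. The difference, its interval and the residual SD will therefore be carried forward.

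**Working it through.** **Inputs from the documents.** 40 randomised 1:1, 10% attrition, two binary stratification factors (four cells if crossed), one baseline covariate per model. The plan's completer count is reproduced: 40 × (1 − 0.10) = 36. No alpha, power, SD or effect size is given for the ANCOVAs, so there is no power figure to reproduce.

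**Assumptions, none in the documents.** Two-sided alpha 0.05; permuted blocks of 2 or 4 within the four cells; binder use 40% and TBI history 30% (20%/20% and 50%/50% also tried with blocks of 4); baseline-outcome correlation 0.6; four random dropouts. R² is the share of the outcome variance left after baseline that the two factors explain together.

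**Degrees of freedom.** The planned model fits intercept, arm and baseline: 36 − 3 = 33. Adding two factors leaves 36 − 5 = 31. The 97.5% t quantile rises from 2.0345 to 2.0395, a ratio of 1.0025. With the small residual imbalance between arms, the interval is 0.8-1.1% wider in simulation when R² = 0 (1.009 with blocks of 4).

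**Expected width ratio, adjusted to planned.** Approximately √(1 − R²) × 1.009. For R² = 0.10: √0.90 × 1.009 = 0.9487 × 1.009 = 0.957.

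**Simulation.** 50,000 trials per setting (30,000 at the alternative prevalences). Width ratios are for blocks of 4 at 40%/30%. Power is for a true effect of 0.8 residual SD, blocks of 4, 10,000 trials.

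| R² | Type I, planned model | Width ratio, simulated | Width ratio, formula | Power, planned to adjusted |
|---|---|---|---|---|
| 0% | 5.0% | 1.009 | 1.009 | 62.1% to 61.5% |
| 2.5% | 4.7-4.8% | 0.996 | 0.996 | not run |
| 5% | 4.5-4.7% | 0.983 | 0.983 | 62.3% to 63.6% |
| 10% | 4.1-4.4% | 0.956 | 0.957 | 62.4% to 66.2% |
| 20% | 3.2-3.6% | 0.901 | 0.902 | 63.0% to 71.8% |
| 30% | 2.4-2.9% | 0.841 | 0.844 | not run |

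The adjusted model holds 5.0-5.1% throughout. Bias of the unadjusted estimate was under 0.003 SD in every setting. Smaller repeat runs gave planned-model type I error of 4.5-4.9% at R² = 5%, 3.9-4.3% at 10% and 3.2-3.5% at 20%, so the effect at 5% is negligible.

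**Standard error against truth.** With perfect balance, the planned model's standard error would exceed the true SD of the estimate by a factor of 1/√(1 − R²): 1.05, 1.12 and 1.20 at R² of 10%, 20% and 30%. Simulated ratios were 1.03, 1.08 and 1.14. They are smaller because incomplete blocks and dropout leave some imbalance.

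**Stable-trait case.** Suppose the factors shift baseline and follow-up equally and explain a share S of the raw variance, with correlation r within strata. The overall correlation is ρ = S + (1 − S)r, and the share of post-baseline residual variance explained is R² = 1 − (1 − S)(1 − r²)/(1 − ρ²). For S = 0.30 and r = 0.6: ρ = 0.30 + 0.42 = 0.72, and R² = 1 − 0.70 × 0.64/0.4816 = 0.070. So 30% of raw variance becomes only about 7% of what is left after baseline.

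- r = 0.6, S = 10/20/30%: interval 0.3-0.4/1.4/2.5% narrower; type I error 4.8-4.9/4.6-4.8/4.5-4.7%.
- r = 0.8: interval changes by 0.5% or less either way.

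If 0.6 is instead read as the overall correlation, within-strata r = (0.6 − S)/(1 − S) is lower. The interval is then 0.4/2.2/4.4% narrower in simulation, so the conclusion is similar.

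**The case against.** The strongest reply is that nothing here is invalid. The planned estimate is unbiased, the test errs on the safe side, and leaving stratification factors out of a pilot of about 36 completers is defensible. That stands, and it limits the point to precision.

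Second, the benefit is conditional and the documents do not establish the condition. They say only that the factors may act on the outcomes, give no strength, and do not say that either predicts change over 30 days. Habitual binder use and past TBI are standing characteristics, so the stable-trait case is the more natural reading, and there the gain is small. This also stands: the 20% and 30% rows need factors that predict change, not only level.

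Third, conservatism depends on balance actually being achieved. The documents describe equal stratification through an automated system but give no block method. Under simple allocation, type I error is about 5% even at R² = 10%, and adjusting costs 3.4% in width if R² = 0. The precision gain nonetheless survives when the factors are prognostic: about 2% at R² = 10% and 8% at 20%.

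Fourth, SCI status is undefined and could mean lesion level or AIS grade. That does not change the conclusion, because the secondary models name no treatment term under any reading. Their bivariate results could tell a later trial whether to adjust, but they do not tighten this trial's estimates.

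**Conclusion.** The concern holds as a modest, conditional point about precision. The factors are in the randomisation and in none of the treatment models. If they explain about 10% or more of the variance left after baseline, and allocation balances them, the planned standard error is noticeably too wide: type I error is 4.1-4.4% rather than 5%, with intervals 4.2-4.5% wider than the allowance that adjustment would remove at 10%, and about 10% at 20%. Below that the effect is negligible, and under a stable-trait reading it probably is. The strength of the factors, their prevalences, the block method and the baseline correlation are all assumed. The change is still worth making because the trade is uneven: about 1% of interval width at risk under stratified allocation, against a gain of several per cent if the factors are prognostic.

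**What to change.** Add regular binder use (yes/no) and TBI history (yes/no) as fixed factors, alongside the outcome's own baseline value, to each ANCOVA: CBF at rest, CBF during testing, cognition, and mood/QOL. Report the adjusted difference, its 95% confidence interval and the residual SD from that model, and name the covariates so that a later trial can be sized for the same analysis.

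The cost is one line of SAP wording and two of 33 residual degrees of freedom. No new data are needed, because both factors must be known at randomisation.
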